3.6. Calculation of the sample size

Based on the sample calculation, the study by Soeding PF et al, 2011 (22) , which observed a drop in MAP under general anesthesia of approximately 30%, the study by Vincent S et al, 2005 (24) , which observed a decrease in MAP under sedation of 5.6%, and the study by Meidert et al 2017 (25) , which observed a decrease in SBP of 18 mmHg and 12 mmHg of MAP in the group with intermittent monitoring in relation to the group with continuous monitoring. Based on these data, a difference in mean total MAP between groups of 12 mmHg was used and therefore, considering the study power of 80% and alpha error of 0.025 by Bonferroni correction due to be divided into 4 groups, a total sample of 92 patients will be need, with standard deviation of the group with continuous monitoring of cardiac output of 10 mmHg and in the group standard monitoring of 15 mmHg. However, estimating that we may have losses, the final sample will reach 100 patients, so there will be 25 patients in each of the 04 groups.

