3.7. Technician

The selected patients will be divided into two groups: group 1 general anesthesia + interscalene brachial plexus block and group 2 sedation + interscalene brachial plexus block. Each group will be divided into two groups, one with hemodynamic continuous monitoring and one with standard hemodynamic monitoring, totaling 4 groups in total in the study. Group 1A general anesthesia + interscalene brachial plexus block with continuous monitoring; group 1B general anesthesia + interscalene brachial plexus block with standard monitoring; group 2A sedation + interscalene brachial plexus block with continuous monitoring; group 2B sedation + interscalene brachial plexus block with standard monitoring (figure 1).

General anesthesia will be done with Propofol (1-3mg/kg), Fentanyl (1-6 mcg/kg) and Rocuronium (0.3-0.6mg/kg) and maintenance of anesthesia will be with Sevoflurane

and Remifentanil. The patient will be maintained on volume-controlled mechanical ventilation (tidal volume 6-8ml/kg, PEEP=5 mmHg, RR=12 ipm, FiO₂=50%) during the procedure. Parameters will be adjusted as assessed by the responsible anesthesiologist.

The technique of interscalene level brachial plexus block will be the same in both groups. The patient will be initially positioned in horizontal dorsal decubitus with the head slightly turned to the opposite side with slight elevation, with palpation of the interscalene groove and introduction of the needle in a slightly dorsal and caudal medial direction. The block will use a short Stimuloplex A50 needle (22G x 2") and the aid of Ultrasonography and peripheral nerve stimulator. The local anesthetic will be 0.5% ropivacaine 15-20 ml.

Sedation will be done with Propofol in a controlled target infusion pump.

The procedure should start about 15 minutes after the end of anesthesia.

Continuous monitoring will be done with clearSight continuously assessing blood pressure, cardiac output and heart rate; NIRS electrode to assess cerebral O₂ saturation, peripheral O₂ saturation, BIS value and axillary temperature.

Standard monitoring will be done with non-invasive blood pressure, heart rate, NIRS electrode to assess cerebral O₂ saturation, peripheral O₂ saturation, axillary temperature, BIS value. In addition, patients will use ClearSight, but the device will be blind to the anesthesiologist. Pressure monitoring will be every 5 min.

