3.10. Data collect

After receiving an explanation about the procedures to be performed and signing the consent form, patients will be allocated into 4 groups as explained above using a table of random numbers. Data collected will be age, weight, height, race, gender, ASA, comorbidities, medications in use. During the surgical procedure, the analyzed data will be medications, infusion volume, blood components, vasopressor, anesthetic and surgical complications, anesthesia and surgery time.

In addition, systolic, diastolic and mean blood pressure, heart rate, cerebral O₂ saturation, peripheral O₂ saturation, axillary temperature, BIS value, cardiac index (in patients who will use clear sight) and et CO₂ (in patients who will be intubated) every 5 min intraoperatively and during post-anesthetic recovery (PAR) (27).

Postoperatively, the data analyzed will be: anesthetic recovery time, hospital stay, need to be referred to the intensive care unit (ICU), length of stay in the ICU and if the patient died. In addition, the visual numerical pain scale and the descriptive verbal pain scale will also be evaluated in the PVR and 24 hours after the procedure (28).

Sedation assessment will be performed using the intraoperative RASS scale for patients who are allocated to the sedation + interscalene brachial plexus block group and postoperatively for all groups. The values of the RASS scale are shown in table 1. The Confusion Management Method in the ICU (CAM-ICU) scale will be used to assess delirium, the table with the parameters used will be shown in figure 5 (29);(30).

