3.13. Data analysis

Categorical variables will be presented as absolute and relative frequencies.

Quantitative variables will be presented as mean and standard deviation or as median and interquartile range when appropriate. We will use the Kolmogorov-Smirnov test to assess the distribution pattern of continuous numerical variables.

Comparisons between general anesthesia + block and block + sedation will be performed, as well as comparisons between standard and continuous monitoring. Proportions will be compared using the Chi-square test or Fisher's exact test, if the assumptions for using the Chi-square are violated. Quantitative variables will be compared using the Mann-Whitney test or irregularly distributed Anova when appropriate.

Variables with repeated measurements will be analyzed by linear general multiple model (GLM) with Bonferroni correction for P values.

The association between explanatory variables and response will be evaluated using logistic regression models. Variables selected in the bivariate analyzes ($p<0.05$) and those considered clinically relevant will be submitted to multiple logistic regression analyses. Variables with substantial collinearity will be excluded. The result of logistic regression analyzes will be expressed as odds ratios and respective 95% confidence intervals.

All significance probabilities (P values) presented will be two-tailed. P values will be considered statistically significant when less than 0.05. *The Statistical Package for Social Sciences* software version 26.0 (SPSS Inc.®; Chicago, IL, USA) will be used to perform the analyses.

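### Section 3.13 analyses 5-minute series of unequal length with an unspecified GLM: use a prespecified mixed model, and fix the window, time zero, MAP device and missing-reading rule with it

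*Combined protocol and SAP*

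**What the plan says.** - Method (3.13): "Variables with repeated measurements will be analyzed by linear general multiple model (GLM) with Bonferroni correction for P values". No covariance structure, time coding, contrast or SPSS procedure is named.
- Schedule (3.10): the haemodynamic and cerebral variables are recorded "every 5 min intraoperatively and during post-anesthetic recovery (PAR"). This is a collection span, not an analysis window. No common number of readings is set, and operative and recovery readings are not separated for analysis.
- Length of series (3.10): the case data include "anesthetic and surgical complications, anesthesia and surgery time", and recovery time is recorded too. No duration is fixed in advance.
- Time zero: the nearest statement is in 3.7, "The procedure should start about 15 minutes after the end of anesthesia". It is not tied to the analysis. The hypotension definition uses an initial MAP without saying when it is taken.
- Device (3.7): standard-monitoring patients have non-invasive pressure every 5 minutes. In addition, "patients will use ClearSight, but the device will be blind to the anesthesiologist". They therefore have two MAP sources.
- Sizing (3.6): "a difference in mean total MAP between groups of 12 mmHg was used". Neither the period nor the device behind that mean is defined.
- Comparisons (3.13): "Comparisons between general anesthesia + block and block + sedation will be performed, as well as comparisons between standard and continuous monitoring". These are the two pooled comparisons; pairwise contrasts among the four groups are not named.

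**The concern.** Two things are at stake.

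The first is precision. A repeated-measures GLM needs a rectangular data set. With series of different length and occasional lost readings, it either drops every patient who lacks a value at any included time point or needs a window short enough to keep most of them. Both waste readings already collected.

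The second is open choices. Which minutes count, from which event and from which device can all be settled after results are visible. Section 3.13 does not say that its Bonferroni correction covers such choices. The schedule in section 5 has data analysis running from month 7 alongside data collection, so outcome data could be examined while the choices are still open.

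**Working it through.** **Plan's own figure.** Inputs from 3.6: difference 12 mmHg, SDs 10 and 15, alpha 0.025 (two-sided, from 3.13), power 80%. The Welch t test (noncentral t) gives 78.0% at 22 per group and 80.1% at 23. So 23 × 4 = 92, as stated. With 25 per group, power is 83.8%.

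The documents give no durations, miss rates or within-patient correlations. Every such value below is an assumption.

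**1. Complete patients.** With independent misses at rate p over k readings, the share complete is (1 − p)^k. With clustered misses (beta-binomial, intraclass correlation 0.2) it is higher.

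| k | p | independent | clustered |
|---|---|---|---|
| 12 | 1% | 0.886 | 0.942 |
| 12 | 2% | 0.785 | 0.887 |
| 24 | 1% | 0.786 | 0.921 |
| 24 | 2% | 0.616 | 0.848 |

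**2. Cost in precision, 24 readings.** The combined SD is √((10² + 15²)/2) = 12.75. With 50 per arm and all patients kept, SE = 12.75 × √(2/50) = 2.55 mmHg. Complete-case analysis multiplies this by about 1/√(share complete):
- independent: 1/√0.786 = 1.13; 1/√0.616 = 1.27
- clustered: 1/√0.921 = 1.04; 1/√0.848 = 1.09

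A generalised least squares calculation for a model with group-by-time terms and a window-averaged effect (random-intercept share 0.3 or 0.5, AR(1) 0.8) agrees. The all-readings SE stays at 2.55, and the ratios are about 1.13 and 1.28 (independent) or 1.04 and 1.09 (clustered).

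**3. Power (Welch, 12 mmHg, two-sided 0.025).** Pooled: 50 × 0.786 ≈ 39 and 50 × 0.616 ≈ 31 complete per arm. Power is 99% at 50, 97% at 39 and 92% at 31. Pairwise: 84% at 25 per group, 80% at 23 and 73% at 20 (25 × 0.786 ≈ 20).

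**4. Window chosen after the data.** 12,000 simulated null trials per setting, 50 v 50, random-intercept share 0.3 or 0.7 plus AR(1) 0.8, normally distributed durations. A t test on the window mean keeps only patients who reach the window, and the smallest P value is compared with 0.05.
- One fixed window: about 5%.
- Best of two (60/90 min with mean duration 120, SD 30; or 30/60 min with mean 90, SD 25): 6.6 to 7.5%.
- Best of three (adding 120 or 90 min respectively): 9.2 to 10.5%.

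**5. Does a mixed model settle the window?** No. Suppose a 12 mmHg effect lasts only for the first 30 minutes (50 per technique, duration mean 90, SD 25, 2% missed, between- and within-patient SDs 9 and 8 mmHg, 150 runs). A random-intercept model with linear time estimates −11.9 mmHg over 0–30 min, −6.1 over 0–60, −4.4 over all readings and −4.1 over 20–60. With a constant effect, all four give about −12. The gap in 3.7 between anesthesia and procedure is 15/5 = 3 readings, so the choice of time zero matters too.

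**6. Selection by duration.** This arises only if duration differs by technique. With assumed means of 120 v 110 or 100 min, SD 30, and duration–MAP correlation r of 0.2 to 0.5, the false difference is r × 12.75 × [m((w − mean₂)/30) − m((w − 120)/30)], where m is the inverse Mills ratio and w the window length. It is 0.02–0.14 mmHg for w = 30, 0.13–0.80 for 60, 0.36–1.98 for 90 and 0.57–2.98 for 120.

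**The case against.** The strongest reply is that GLM is loose, possibly translated wording. Section 3.13 names SPSS but no procedure, so complete-case loss is not established. That stands: items 1 and 2 apply only under the repeated-measures reading. The missing window, time zero and device matter under any reading.

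A second reply is that writing these choices down is what closes them, and that the mixed model is a preference. Item 5 supports the first half. The model's own contribution is to keep patients with missed readings; it does not choose the window. A patient-level mean over a fixed window analysed by ANCOVA would also do, and it sits closer to the mean on which the trial was sized.

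A third reply is that section 3.11 has the data analysed with groups shown only as numbers. This limits choosing a window to favour a technique. It does not prevent trying several windows and keeping the smallest P value.

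A reader might go further and infer that the main comparisons are underpowered, or that results will be biased toward one technique. The documents support neither. Pooled power stays at 92% or more in the cases computed. Only pairwise contrasts, which 3.13 does not name, fall below 80%. Selection bias needs a duration difference that the documents do not show, and in the cases computed it stays at or below 3.0 mmHg against the planned 12.

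**Conclusion.** The point holds, as something that should be changed rather than a fatal flaw. The plan sends unequal 5-minute series to an unspecified model and sets no window, time zero, MAP device or missing-reading rule.

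On the natural reading of GLM, the avoidable loss is about 13 to 28% in standard error with independent misses of 1 to 2% over 24 readings, and about 4 to 9% with clustered misses. The main reason to act is the open choices. If several windows were tried and the best kept, the false-positive rate would be about 7 to 10%. This is conditional: it should not be read as saying that the planned analysis has an inflated error rate, or that anyone intends such a search. All sizes rest on assumed durations, miss rates and correlations. That series will differ in length is itself an inference, though a sound one, because case times are recorded per patient and nowhere fixed.

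**What to change.** In 3.13, replace the GLM with a linear mixed model, in the same software, on all available intraoperative readings:
- patient random intercept and a named residual covariance (for example AR(1));
- categorical 5-minute time;
- technique, monitoring, their interaction with each other, and the interaction of each with time;
- the initial value as covariate, taken at one stated moment before anesthesia.

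Before any outcome data are examined, also fix:
- one named event, present in all four groups, as time zero;
- one analysis window, preferably one that nearly all operations will reach;
- the same MAP device in all four groups;
- the missing-reading rule: missed readings stay missing, and times after surgery has ended are not counted as missing.

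Name a single primary MAP summary: the technique and monitoring effects averaged over that window, with the mean total MAP of 3.6 defined to match. Label any whole-operation mean or early-window analysis as sensitivity only. Model recovery separately.

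A patient-level mean over the fixed window with ANCOVA is an acceptable simpler alternative. If the GLM is kept, the minimum is to prespecify time zero, the window and the missing-reading rule.

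Cost: wording in 3.13 and 3.6, and keeping the clock time of the chosen event if only durations are now recorded. There are no extra patients or readings. Downsides: slightly more modelling work, a covariance choice made in advance, and reliance on missing at random for missed readings. That assumption does not cover times after surgery has ended.

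### Bonferroni, the only multiplicity correction named, is valid and meets the planned 80% power; Holm's step-down version would be a cheap, optional gain in efficiency

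*Combined protocol and SAP*

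**What the plan says.** Section 3.6 (sample size) uses an "alpha error of 0.025 by Bonferroni correction due to be divided into 4 groups". The other inputs are 80% power ("considering the study power of 80" per cent), an effect stated as "a difference in mean total MAP between groups of 12 mmHg was used", a "standard deviation of the group with continuous monitoring of cardiac output of 10 mmHg" and "in the group standard monitoring of 15 mmHg". From these the plan reaches "a total sample of 92 patients will be need", and with an allowance for losses "the final sample will reach 100 patients, so there will be 25 patients in each of the 04 groups".

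Section 3.13 (data analysis) names two comparisons: general anesthesia against sedation, and standard against continuous monitoring. Repeated measurements go into a "linear general multiple model (GLM) with Bonferroni correction for P values". The number of tests covered by that correction is not given. For the Chi-square, Fisher, Mann-Whitney and Anova comparisons no correction is named, and significance is declared at a two-tailed 0.05.

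**The concern.** Wherever the plan corrects for multiplicity it uses plain Bonferroni. For any fixed family of tests, Holm's procedure controls the same familywise error, needs no assumption about how the tests are related, rejects everything Bonferroni rejects, and sometimes rejects more. With two tests, the smaller P value is compared with 0.025; if it is significant, the other is compared with 0.05 instead of 0.025.

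This trial has two randomised contrasts, and section 2.2 lists superiority of continuous monitoring as an objective. If technique has a clear effect on MAP and monitoring a modest one, monitoring is the contrast that would benefit. At stake is some power on whichever contrast has the larger P value. Error control and the chance of at least one significant result are not affected.

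**Working it through.** **Inputs.** From 3.6: difference 12 mmHg, SD 10 (continuous) and 15 (standard), alpha 0.025, power 80%, 92 patients (23 per group), raised to 100 (25 per group). From 3.13: two-tailed tests, two named comparisons. Inferred: a family of two, since 0.05/2 = 0.025. Assumed: the two tests are independent, and the other contrast is either real or null as stated.

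**1. The plan's own figure.** Two-sample t-test with unequal variances (Welch), noncentral t:
- SE = √((10² + 15²)/23) = √(325/23) = 3.76 mmHg; noncentrality 12/3.76 = 3.19; about 38 degrees of freedom.
- At alpha 0.025, power is 80.1% with 23 per group and 78.0% with 22. So 23 × 4 = 92, an exact match.
- With 25 per group, power is 83.8%.

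The cost of Bonferroni is therefore already paid for in the 92.

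**2. Holm for two tests.** Let p be a contrast's power at 0.025, q its power at 0.05, and r the chance that the other contrast is significant at 0.025. Then

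power under Holm = p + (q − p) × r.

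**3. One contrast of 23 vs 23 at 12 mmHg** (p = 0.8010, q = 0.8752):
- Other 12 mmHg effect real, r = 0.801: 0.8010 + 0.0742 × 0.801 = 0.860.
- Other effect null, r = 0.025: 0.8010 + 0.0742 × 0.025 = 0.803.
- At least one rejection, both real: 1 − (1 − 0.801)² = 96.0% under either method.
- Both rejected, both real: Bonferroni 0.801² = 64.2%; Holm 0.801² + 2 × 0.801 × 0.0742 = 76.1%.

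For 80% power per contrast under Holm, the total stays at 92 if the other effect is null. It falls to 84 (21 per group) only if the other 12 mmHg effect is taken as real.

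**4. The monitoring contrast over all four groups** (50 vs 50). SE = √(325/50) = 2.55 mmHg.

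| True monitoring difference | Bonferroni | Holm, technique effect 12 mmHg | Holm, no technique effect |
|---|---|---|---|
| 12 mmHg (the plan's) | 99.2% | 99.6% | 99.2% |
| 8 mmHg (assumed) | 80.2% | 87.3% | 80.4% |
| 6 mmHg (assumed) | 53.1% | 64.2% | 53.4% |

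For the 8 mmHg row, p = 0.8024, q = 0.8734 and r = 0.9917, so 0.8024 + 0.0710 × 0.9917 = 0.873; with r = 0.025 the result is 0.804. A technique effect above 12 mmHg changes little, since r is already 99%. Simulation of the four groups agrees to within about 0.2 points. On the 92 patients before losses (46 vs 46), the 12 mmHg figures are 98.6% and 99.4%.

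**5. The repeated-measures model.** No figure can be given. The documents state neither the number of corrected tests nor the within-patient correlation.

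**6. Tests outside that model.** Two independent tests each at 0.05 have a familywise error of 1 − 0.95² = 9.75%. No power is given away there, because no correction is applied.

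**The case against.** The strongest case against is that this is a preference between two valid methods. Bonferroni delivers the planned power, Holm's first step also uses 0.025, and at the plan's own 12 mmHg the pooled monitoring contrast is already above 99%. Bonferroni also has matching simultaneous confidence intervals, and Holm has no simple equivalent. All of this stands, and it is why the point is optional.

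Four stronger readings are tempting, and the documents do not support them.
- *The trial loses planned power.* It does not: 92 reproduces at alpha 0.025.
- *Every corrected comparison in the model loses power.* It does not: Holm treats the smallest P value exactly as Bonferroni does.
- *The contrast tested second has 87.5% power.* That is the power of a 23 vs 23 test at 0.05, reached under Holm only if the other hypothesis is certain to be rejected. Nor is the contrast tested second fixed in advance; it is whichever has the larger P value.
- *The protocol's inputs guarantee a large technique effect.* Section 3.6 sets a MAP fall of about 30% under general anesthesia against 5.6% under sedation. The Introduction, however, reports a near-identical 5.7% from the same sedation series as an incidence of hypotension or bradycardia. That figure is not a safe basis for sizing the technique effect.

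The opposing case also points to a nearby gap: 3.6 uses 0.025, while 3.13 declares significance at 0.05 with no correction outside the repeated-measures model. For those tests Holm would be stricter than the present text. That is a reason to define the family, not a reason against Holm.

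**Conclusion.** The point holds as an optional efficiency improvement; there is no error in the plan. Holm gives the same error control with never less power.

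The size of the gain rests on a family of two, on independent tests, and above all on whether the other contrast is real. It is about 0.2 to 6 points for a 23 vs 23 contrast at 12 mmHg. For the pooled monitoring contrast it is under 1 point at 12 mmHg. The 7 and 11 point gains need true differences of 8 and 6 mmHg, which the documents do not state, together with a technique effect of about 12 mmHg or more. Without a technique effect they shrink to 0.2 or 0.3 points.

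**What to change.** - In 3.13, replace the Bonferroni correction of P values with the Holm step-down correction, and list the tests in the family.
- For mean MAP, state the rule for the two randomised contrasts (technique, monitoring): compare the smaller P value with 0.025 and, if it is significant, the other with 0.05. This also brings 3.13 into line with the 0.025 in 3.6.
- In 3.6, keep the sample size and describe the stated 80% as the minimum power per contrast on the plan's inputs. Do not state 87.5%.
- Say how confidence intervals will be reported: either kept at the Bonferroni level or labelled unadjusted.

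The cost is a change of wording. No extra patients or data are needed, and Holm-adjusted P values follow directly from the unadjusted ones. The one real downside is the lack of simple matching simultaneous intervals.

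### The multiple logistic model is built by a bivariate P<0.05 screen and an undefined relevance route, without guaranteeing that technique and monitoring stay in or keeping post-randomisation variables out

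*Combined protocol and SAP*

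**What the plan says.** Section 3.13 introduces the model in general terms: "The association between explanatory variables and response will be evaluated using logistic regression models". It names neither the response nor the explanatory variables. Entry is by two routes. One is "Variables selected in the bivariate analyzes" at P<0.05. The other is stated as "and those considered clinically relevant will be submitted to multiple logistic regression analyses", with no list and no criterion. A removal step follows, with no threshold: "Variables with substantial collinearity will be excluded". Results are to be "expressed as odds ratios and respective 95% confidence intervals", with no allowance for the selection.

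The same section plans the randomised contrasts separately: "Comparisons between general anesthesia + block and block + sedation will be performed, as well as comparisons between standard and continuous monitoring". Proportions go to chi-square or Fisher tests. For serial data it says: "Variables with repeated measurements will be analyzed by linear general multiple model (GLM) with Bonferroni correction for P values".

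Section 3.10 gives the data items. Eight are baseline (age, weight, height, race, gender, ASA, comorbidities, medications in use). The intraoperative ones are described thus: "During the surgical procedure, the analyzed data will be medications, infusion volume, blood components, vasopressor, anesthetic and surgical complications, anesthesia and surgery time". Nothing in 3.13 excludes the intraoperative items as explanatory variables.

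**The concern.** In a randomised trial, a multivariable model that may be read as giving the effect of technique or monitoring should contain those two factors by design. Here their presence depends on a significance test or on a judgement that is not written down. A factor kept because it was significant tends to have an overstated odds ratio, and its interval is computed as if no selection had taken place.

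The second problem is what may sit beside the factors. Section 3.7 gives fluid, ephedrine and transfusion in response to hypotension, and the triggers differ between the monitoring arms. Section 2.2 treats vasopressor use, transfusion and infused volume as results to be related to monitoring. In a model of hypotension or low cerebral saturation these variables are consequences of the arm, and partly of the outcome itself. They could readily pass a P<0.05 screen, and adjusting for them would distort the randomised effect.

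The collinearity rule adds to this. Section 3.7 specifies some drugs only for general anesthesia, and 3.10 records etCO₂ only in intubated patients. Technique can therefore be collinear with its own components, and nothing says which variable is removed.

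**Working it through.** **The plan's own figure.** The only computed figure is the sample size in 3.6; the logistic model has none. With a difference of 12 mmHg, SDs of 10 and 15 mmHg (root mean square √((100+225)/2) = 12.75), two-sided alpha 0.025 and 80% power, the noncentral t calculation gives 23 per group, and 4 × 23 = 92, as stated. It does not bear on this point except to fix the final size: 100 patients, 25 per cell, so 50 against 50 for each randomised factor.

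**Assumptions.** The documents give no event rate, odds ratio or covariate effects for a logistic outcome. Assumed: control rate 30% (20% as a sensitivity case), true technique OR 1 to 4, independent covariates, and the P value as the only gate.

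**Step 1: chance that technique fails the screen, by formula.** For OR 2 the other arm's odds are (0.30/0.70) × 2 = 0.857, so its rate is 0.462. The difference is 0.1615 and the mean rate 0.381.
- Null SE = √(2 × 0.381 × 0.619/50) = 0.0971.
- Alternative SE = √((0.210 + 0.2485)/50) = 0.0958.
- z = (0.1615 − 1.96 × 0.0971)/0.0958 = −0.30, so power is 38% and the chance of being dropped is 62%.

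The same steps for OR 3 (rate 0.5625) give 24%. At a 20% control rate the figures are 68% and 30%.

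**Step 2: simulation of the whole rule.** N = 100 in the 2×2 layout; a univariable P<0.05 screen, then a multiple logistic fit of the survivors. Two covariate sets were used: 8 covariates (two with OR 1.49 per SD) and 15 unrelated covariates. The 8-covariate set with 4,000 trials per scenario and a 30% control rate gave:

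| True technique OR | Dropped | Median OR when kept | 95% interval coverage when kept |
|---|---|---|---|
| 1.5 | 85% | 2.9 | 83% |
| 2.0 | 66% | 3.0 | 93% |
| 3.0 | 26% | 3.5 | 97% |
| 4.0 | 10% | 4.2 | 98% |

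Across the formula and both covariate sets at a control or event rate of 30%, the drop rate is about 60 to 66% at OR 2 and about 21 to 31% at OR 3.

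**Step 3: is the inflation due to selection?** At OR 3, fitting every candidate without a screen also gives a median of 3.5 with 8 covariates, and 4.0 with 15. At OR 4 the unscreened median is 4.8, above the 4.2 after screening. So at OR 3 and above, the excess comes from a crowded model in 100 patients. Selection adds inflation for weak and moderate effects.

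**Step 4: null variables.** If technique has no effect but passes the screen, its interval covers OR = 1 in 17% of cases. Across all null variables that pass, with technique OR 1 to 4, coverage is about 12 to 33%. This is close to automatic, because they were kept for having P<0.05.

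**Step 5: false predictors.** At least one noise covariate is significant in the final model in 43 to 49% of screened models with 15 candidates, against 62 to 63% of unscreened ones. With 8 candidates the figures are 27 to 31% against 37%. Simple arithmetic gives the same order: 1 − 0.95^15 = 54% and 1 − 0.95^8 = 34%. The number of candidates drives this.

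**Step 6: with both factors forced in** (covariates still screened), the median technique OR is 2.02 with 95.4% coverage at true OR 2, and 3.06 with 94.3% at true OR 3.

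**The case against.** The strongest reply is that the randomised comparison does not depend on this model. Section 3.13 plans direct tests of both factors and a linear model for repeated measures; randomisation makes the unadjusted contrast valid, and the sample size rests on MAP. That stands. A reader might infer that the screen could lose the trial's treatment comparison, or that logistic regression is the only analysis of binary outcomes. The documents support neither. It remains true that 3.13 specifies an interval only for the logistic results, that this is its only multivariable model for a binary response, and that it does not call the model exploratory.

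Second, the clinical-relevance route could keep technique and monitoring whatever their P values. That also stands: the drop rates describe the screen acting alone. The route is undefined and does not name the two factors, so their retention is possible but not assured.

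Third, 3.13 names no response, and 3.10 lists data to be collected, not declared predictors. Which outcomes and covariates would be used is therefore inference, and the effect of adjusting for post-randomisation variables has not been quantified. The text does nothing to prevent it.

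Two further inferences should be resisted. The 95% intervals do not fail in general: for a kept OR of 2 or more, coverage is near nominal. Nor does the screen create false predictors: Step 5 shows fewer with it than without it.

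**Conclusion.** The point holds in a limited form. The plan states a data-driven selection rule that gives a worse adjusted estimate than a fixed model would. What is at risk is the adjusted odds ratio for technique or monitoring, and any independent-predictor claim.

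If the P value alone decides entry, a moderate technique effect (OR 2) is more likely to be dropped than kept, at about 60 to 66%, and reads as about 3 when kept. At OR 3 the drop rate is about 21 to 31%, with little inflation attributable to selection. Intervals fall well short mainly for null or weak variables that pass; for a kept OR of 2 or more, coverage is about 93 to 97%.

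These sizes rest on the assumed 30% event rate, the assumed odds ratios and independent covariates; correlated covariates would change them. Three facts need no assumption: the relevance route is undefined, the randomised factors are not guaranteed a place, and post-randomisation variables are not barred.

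**What to change.** Name the binary outcomes to be modelled by logistic regression. For each, replace the bivariate P<0.05 screen with one model that always contains technique and monitoring, plus a short list of baseline covariates fixed before the data are seen. That list should take the place of the open clinical-relevance route. Deleting the screen alone is not enough, since a model holding every candidate has its own inflation and more false predictors.

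Exclude post-randomisation variables (infusion volume, blood components, vasopressor, anesthesia time) from any model that estimates a technique or monitoring effect, and state that the collinearity rule cannot remove a randomised factor. If a screened risk-factor search is still wanted, report it separately and label it exploratory.

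The cost is a change of wording in 3.13, with no new data or patients. The downside is a shorter exploratory predictor list.
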